2.1 Primary Objective

The primary objective of this study is to evaluate the endoscopic removability of the stent component of the Evolution® Esophageal Stent System – Fully Covered (known as the Evolution® Esophageal fully covered stent) when used to treat patients with an obstruction caused by an intrinsic or extrinsic malignancy; refractory benign esophageal strictures; or esophageal fistulas, perforations, or leaks.

The **primary endpoint** will be the proportion of patients, of those patients in whom endoscopic retrieval is attempted after an indwell time of between 7 days and 6 months, who have successful stent removal (see Appendix C) of the Evolution® Esophageal fully covered stent. [REDACTED]

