5.5 Endpoints

5.5.1 Primary Endpoint

Since the objective of the study is to evaluate endoscopic removability of the stent when used as intended, the **primary endpoint** will be the proportion of patients, in whom retrieval is attempted endoscopically after an indwell time between 7 days and 6 months, who have successful removal (see Appendix C) of the Evolution® Esophageal fully covered stent.

[REDACTED]

[REDACTED]

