6.5 General Analysis

The first 58 patients with attempted endoscopic stent removal (see Appendix C for definition) after an indwell time of at least 7 days, but no more than 6 months, will be included [REDACTED]. It is recognized that additional patients enrolled prior to the 58th attempted endoscopic stent removal may also have stent removal attempted prior to exiting the study. Those additional patients will be followed until reaching a study endpoint; however, these patients will not be initially included [REDACTED]

Secondary endpoints may be analyzed separately and/or together for those patients with attempted stent removal compared to those patients without attempted stent removal. [REDACTED]

Descriptive summaries will be provided where appropriate for each of the primary and secondary variables. In general, summaries will be complete over the total population. Continuous variable summaries will include the number of subjects (N), mean, standard deviation, minimum, and maximum. Categorical variable summaries will include the frequency and percentage of subjects who are in the particular category. In general, the denominator for the percentage calculation will be based upon the total number of subjects with the measurement for the total population and by treatment group, unless otherwise specified.

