¹ If a non-study stent is placed (e.g., inside the study stent or after study stent removal) or if the study stent is removed surgically, patient will exit the study immediately. If study stent is completely removed endoscopically and not replaced, patient will be followed for 30 days. If stent is not completely removed and non-study stent is not placed, patient will be followed until patient reaches 6-month follow-up or stent is completely removed.

² Additional endoscopy and/or radiographic assessment (e.g., X-ray) should be performed if clinically indicated (e.g., lack of marked improvement in dysphagia score, significant pain, suspected stent migration). Additional X-rays may be warranted in patients at higher risk for migration.

³ If stent placed for fistula, perforation, or leak, radiographic assessment (e.g., barium swallow) should be performed to confirm successful sealing of the lesion after stent implantation and to confirm lesion closure following stent removal.

⁴ Patient will be requested to provide information regarding clinical symptoms (e.g., dysphagia) and adverse event information since the last contact, if applicable, during each telephone contact and clinical visit during the patient’s study participation. Adverse events should also be reported upon awareness of the event if between telephone contacts and clinical visits.

For patients with a fistula, perforation, or leak, documentation of the original lesion closure should be obtained following stent removal (e.g., barium swallow), even if the original lesion is not identified using endoscopy at stent removal.

Additional endoscopy and/or X-rays should be performed according to standard of care if clinical symptoms persist/recur (e.g., lack of marked improvement in dysphagia score, significant pain, suspected migration). Additional X-rays may be warranted in patients at higher risk for migration (e.g., patients undergoing radiation/chemotherapy, patients with gastric surgery resulting in altered anatomy). Symptoms resulting in additional endoscopies should be recorded as adverse events.

At follow-up, the following information should be recorded, at a minimum:

- Dysphagia score
- Patient’s resumption of oral intake
- Current clinical symptoms (e.g., pain, nausea)
- Adverse events (including serious events) since last contact

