7.8 Stent Removal

Patients will have the stent removed when it is clinically indicated based on the physician’s clinical judgment. Please refer to the manufacturer’s IFU for information regarding stent removal. The indwell time may be different depending on the indication for stent implantation.

[REDACTED]

There is a lasso loop with a grasping feature on both ends of the stent to allow stent removal. If the stent is endoscopically removed, the patient will be followed for 30 days post-stent removal unless a new, non-study stent is placed. If the stent is removed surgically (e.g., during esophagectomy), the patient will exit the study immediately.

If the stent is unable to be completely removed during the initial removal procedure, the patient will continue to be followed until the stent (or remainder of the stent) is removed, until an additional stent is implanted, or for 6 months after the initial stenting procedure, whichever comes first.

If the stent is endoscopically removed, the following information should be recorded, at a minimum:

- Reason for removal
- Dysphagia score (prior to stent removal)
- Ability to completely remove stent
- Device integrity
- Adverse events since last contact and during removal procedure (including serious events and visible tissue damage or hemorrhaging requiring immediate intervention)

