APPENDIX C

Definitions

Attempted stent removal/retrieval: an endoscopic procedure in which one of the following occurs:

- 1) Removal is attempted by grasping the green lasso or other portion of the stent with the intention to remove the stent, or
- 2) Removal is intended, but the subject is not considered to be a candidate for safe endoscopic stent removal (i.e. endoscopic removal is felt to be not possible or not safe)

Clinical success, for patients with obstruction caused by an intrinsic or extrinsic malignancy or patients with a refractory benign esophageal stricture: improvement or relief of dysphagia symptoms at the 7-day post-stent follow-up

Clinical success, for patients with a fistula, perforation, or leak: seal sufficient to enable oral intake at the 7-day post-stent follow-up

Dysphagia score: ■

- 0 = able to eat a normal diet
- 1 = able to eat some solid food
- 2 = able to eat some semi-solid food only
- 3 = able to swallow liquids only
- 4 = inability to tolerate any oral intake

Significant dysphagia ≥ 2

Dysphagia, improvement: a decrease in the dysphagia score by at least 2

Dysphagia, relief: complete relief of dysphagia (i.e., dysphagia score of 0)

Stent migration: migration of the stent such that it is no longer covering treated lesion

Stent removal-related adverse events: an adverse event directly related to the endoscopic removal of the stent. These events include esophageal perforation, esophageal tears, and esophageal bleeding requiring immediate intervention. If these conditions were present prior to stent placement, any worsening due to stent removal would be considered related to the removal procedure. However, an adverse event identified during the removal procedure that was not caused specifically by removing the stent will be reported separately. For example, an ulceration or perforation that arose during implantation would not be considered as associated with

removal. Also, events caused by either applying or removing a method of supplemental fixation will not be considered related to stent removal.

Successful stent removal: one in which the Evolution® Esophageal fully covered stent

- 1) Is completely removed from the patient during a single endoscopic procedure with the wire mesh integrity maintained such that the stent can be removed in one contiguous piece, and
- 2) Has no tissue damage or hemorrhage visible during the retrieval procedure that is both:
 - a. Related to endoscopic stent removal and

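### When a patient has more than one removal attempt, is it open which attempt decides the primary endpoint?

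*Combined protocol and SAP*

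**What the plan says.** Sections 2.1, 5.5.1 and 6.1.1 count patients. In 2.1 the numerator is those "who have successful stent removal (see Appendix C) of the Evolution" stent, and in 5.5.1 the denominator is those "in whom retrieval is attempted endoscopically after an indwell time between 7 days and 6 months". Section 6.5 takes "The first 58 patients with attempted endoscopic stent removal (see Appendix C for definition) after an indwell time of at least 7 days" and no more than 6 months.

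Appendix C works by procedure. An attempt is an endoscopic procedure in which the stent is grasped with intent to remove it, or one in which "Removal is intended, but the subject is not considered to be a candidate for safe endoscopic stent removal". A success has two conditions. The stent "Is completely removed from the patient during a single endoscopic procedure with the wire mesh integrity maintained", so that it comes out in one contiguous piece, and the removal "Has no tissue damage or hemorrhage visible during the retrieval procedure that is both" related to the removal and in need of immediate treatment.

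The plan expects that some first attempts will not finish the job. Section 7.8 says: "If the stent is unable to be completely removed during the initial removal procedure, the patient will continue to be followed until the stent" or its remainder is out, another stent is implanted, or 6 months have passed. Footnote 1 of Table 2 is similar: "If stent is not completely removed and non-study stent is not placed, patient will be followed until patient reaches 6-month follow-up" or the stent is completely removed.

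**The concern.** The unit of analysis is the patient and the unit of definition is the procedure, and no readable sentence joins them for a patient with two procedures. In 6.5 the word first selects patients, not attempts within a patient.

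Consider a patient whose stent is grasped but not freed, or judged unsafe to remove, and is then taken out whole and without treated injury some weeks later. If the single-procedure condition means that one procedure sufficed, the patient is a failure. If it means only that the extraction itself was not staged, the patient is a success. The injury condition raises a similar question about treated damage at the failed attempt.

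The lenient reading can only raise the success rate. The study is single-arm and unblinded (5.7), so a reading could in principle be chosen after the results are known. With 58 patients and a goal of 88%, one patient can decide the test.

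**Working it through.** **1. Which patients the two readings separate**

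| First qualifying attempt | Later course | One procedure must suffice | Any clean removal counts |
|---|---|---|---|
| Stent fractured or out in pieces | any | failure | failure |
| Stent out whole, injury treated | none | failure | failure |
| Judged unsafe or not possible | never removed endoscopically | failure | failure |
| Stent left whole | later out whole, no treated injury | failure | success |

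Only the last row differs. To reach it, a patient must not have had surgical removal or a non-study stent, either of which ends participation at once (7.6, 7.10), and must have a second endoscopic procedure before study exit at 6 months.

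**2. Which reading the text supports**

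- A stent that leaves the body in one contiguous piece will ordinarily have left in one procedure. On the lenient reading the single-procedure condition therefore adds almost nothing to the one-piece condition. It does real work only if it excludes patients who needed more than one procedure.
- The second limb of the attempt definition puts into the denominator a procedure at which the stent was not removed. That procedure cannot be a success. Letting a later one cancel it would undo the purpose of the limb.
- An attempt under the heading of removal/retrieval is itself an endoscopic procedure, so damage treated at a failed attempt is damage at a retrieval procedure. Section 5.6 lists tissue damage and hemorrhage needing immediate intervention among the primary-endpoint variables.

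**3. Size, if the lenient reading were used**

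Inputs from the documents: n = 58 (6.2) and goal 88%, with the alternative above it (6.1.1). The test, alpha, power and assumed true rate are redacted, so the plan's 58 cannot be reproduced. I assume a one-sided exact binomial test at 0.025 or 0.05.

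Pass mark, with X ~ Bin(58, 0.88):

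- P(X ≥ 56) = 0.0006 + 0.0048 + 0.0185 = 0.0239
- P(X ≥ 55) = 0.0239 + 0.0471 = 0.0710

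The mark is 56/58 at either alpha. A score test gives the same mark (p = 0.0225 at 56 and 0.0548 at 55). A Wald test moves it to 55 (p = 0.0094, against 0.0625 at 54).

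Let r be the share of all first-attempt failures that the lenient reading would score as successes. With a true first-attempt rate of 0.88, the scored rate is 0.88 + 0.12r. The documents give no value for r, so these are assumptions:

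| r | Scored rate | P(X ≥ 56) |
|---|---|---|
| 0 | 0.880 | 0.0239 |
| 0.05 | 0.886 | 0.0320 |
| 0.10 | 0.892 | 0.0426 |
| 0.125 | 0.895 | 0.0491 |

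Here r is a product: the share of failures that leave the stent whole and the patient uninjured, times the share of those later removed cleanly. The last row is 0.5 × 0.25 = 0.125.

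**The case for a change.** The strongest argument for a change is that the plan foresees a second procedure and never says in readable text how to score it. The lenient reading is also grammatically possible: a stent freed at the second attempt did come out during one procedure. That much stands. A sentence naming the first qualifying attempt would cost little.

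It can be added that landing one short of the mark is not rare. The probability of exactly 55/58 is 0.23, 0.21 or 0.16 at true rates of 95%, 96% or 97%. At those rates, however, the device does exceed 88%, so a flip there would not be a false claim. That one patient can tip the result holds for any pass mark with 58 patients and is not peculiar to this gap.

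The false-positive argument needs the null rate, a lenient analyst and a sizeable r together. If alpha is 0.025, even r = 0.05 takes the pass chance above it (0.0320). If alpha is 0.05, every row of the table stays below it. Larger shares would do more harm: r = 0.25 gives 0.0965. Nothing in the documents supports a share that high, and fractures and treated injuries, which cannot convert, hold r down.

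Finally, the redactions stand next to the endpoint and in the analysis and removal sections. Words blacked out there cannot be treated as absent from the plan.

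**Conclusion.** This is an unwritten detail with a sensible default, not a stated rule that gives a wrong answer. The single-procedure condition and the inclusion of abandoned removals as attempts both lead an analyst to score a patient whose first qualifying attempt failed as a failure, whatever happens later. Under that scoring the exact type I error is 0.0239 at a pass mark of 56/58.

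The opposite scoring would affect one narrow group and, for assumed shares of 5% to 12.5% of failures, would raise the chance of passing at a true rate of 88% to between 3.2% and 4.9%. This rests on an assumed exact one-sided test and an assumed share, since the documents show neither. Writing the rule down would record the reading already favoured and would not alter the design, the sample size or the expected analysis. No change to the plan is needed.
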